### 9.0 Process to Document Consent: Procedure for Consent

- The person obtaining informed consent will:
  - Introduce themselves to the potential subject
  - Provide an explanation of a) what clinical research is and why you are approaching them; b) why people generally volunteer to participate in research; c) what they can expect if they choose to participate in clinical research; d) how participating in the study will not affect their regular care or relationships with their care providers.
  - Explain that research staff will look into their medical records to confirm their past/current mental health diagnosis and that HIPPA Authorization is being obtained.
- After explaining the principles above, the person obtaining informed consent will:
  - Ask the potential subject if they want to hear the details about the particular research and answer any questions that may arise.
  - Acknowledge that the potential subject verbalized understanding of the research and research related procedures.
  - Explain to the potential subject that signing ICF is entirely voluntary.
  - Explain to the potential subject risks and benefits of participating in the particular protocol.
  - The potential subject, or legally authorized representative, will;
    - be given ample time to completely read and/or listen to the consent form being read to them and ask any questions.
- The subject and the person obtaining informed consent will sign and date the last page of the consent form if they wish to participate in the study.
- A witness signature will be obtained in order to be in compliance with Illinois law pertaining to the utilization of mental health information from a HIPAA covered record.
- A copy of the fully signed consent form will be given to the subject.
- Copies will be filed in the subject's research file.
- The ICF process will be documented in the study source document by the person who is obtaining the consent.
- If during the course of the research trial, the informed consent form is revised, subjects will be re-consented using the revised IRB approved consent form, if applicable subjects will be re-consented after each IRB Continual Review with a newly IRB approved ICF even though it does not reflect any changes in the study protocol.
- Those who were consented before the study was determined to meet the definition of an NIH-funded clinical trial will be given a document at their next study visit that contains information about what this means and includes the clinicaltrials.govidentification number.

### **10.0 Risks to Participants:**

Potential Risks and Protections in Place Against Foreseeable Risks. The potential risks of this project are minimal. The possibility exists that participants may become bored or fatigued during: 1) pre-test and post-test role-plays; 2) VR training; 3) cognitive assessments; 4) vocational history interview; or 5) mental health history

interview. In response, we will include scheduled and unscheduled breaks to protect against these risks. To minimize the risk of possible fatigue and/or boredom, breaks will be scheduled between assessments in long sessions and between role-plays, and participants will be reminded that they can request a break at any time during. Should a research staff member notice signs of fatigue and/or boredom from a participant, an unscheduled break will be taken. The research team has used these procedures for other studies, and they have been effective at reducing risks of fatigue and/or boredom for study participants.

There is a very low risk that participants could be distressed by the mental health interview or job interview role plays. If this happens, participants will be asked to take a break and be offered the chance to drop out of the study if these aspects of the study are too distressing for them. Of the more than 150 participants who completed the mental health interview and four role-plays each during the efficacy studies (600 total role-plays), no participants reported feeling distressed by the interview or role-plays.

These risks will be reviewed during the discussion regarding informed consent, and researchers will take all possible precautions to minimize these potential risks. Moreover, only personnel trained in interviewing and testing protocols with individuals 18 year and older will conduct these procedures.

Although there are no known adverse or severe adverse events that have occurred as a result of using the training, it is possible that a participant could arrive to a research visit (or escalate during a research visit) in a way that is symptomatic or suicidal during the course of the study. Per Thresholds and NU policies, both sites will have clinical staff available (including the PI, [name]) to assess the mental health and the risk of harm to self or others. If trained research staff observe a participant to be highly symptomatic or suicidal then they will follow the following policies at NU and Thresholds:

### If SCID-V has been administered:

- If a participant endorses suicidal ideation and behavior within past 30 days by any of the following items:
  - o item OP8, "Suicidal ideation lifetime" [if within last 30 days],
  - o item OP9, "Suicidal ideation pastweek,"
  - o item OP13, "Suicide attempt lifetime" [if within last30 days], OR
  - o item OP14, "Suicide attempt past week"),

proceed to administer the Columbia Suicide Severity Rating Scale (C-SSRS) as instructed below.

• If participant does not meet any of the criteria above on the SCID-V, continue with study procedures per protocol.

### If Beck Depression Inventory has been completed:

- For item 9 of the Beck Depression Inventory (self-report), if a participant endorses a rating a rating of 2 "I would like to kill myself," or 3 "I would kill myself if I had the chance," proceed to administer the Columbia Suicide Severity Rating Scale (C-SSRS) as instructed below.
- If participant does not meet the cutoff score on item 9 of the BDI, continue with study procedures per protocol.

### If participant endorses distress during other procedures (i.e., during job-interview roleplays):

- Ask the participant if he/she would like to take a break and if the participant has any concerns about completing the [i.e., roleplay, survey].
- If participant indicates willingness to proceed, continue with study procedures per protocol.
  - Participant will be given option to reschedule remaining study procedures for another date, if preferred by participant.
- If participant indicates distress, proceed to administer Brief Psychiatric Rating Scale (BPRS) and/or Page 20 of 34

Columbia Suicide Severity Rating Scale (C-SSRS) as appropriate, as instructed below.

# If suicidal ideation is detected (based on Beck Depression Inventory item 9 cut-off score of 2 or 3, OR other indication):

- Administer the Columbia Suicide Severity Rating Scale (C-SSRS). If participant scores 4 or higher on the "intensity of Ideation" section, proceed with emergency procedures.
  - If participant scores below 4, continue with study procedures per protocol and notify primary Thresholds research staff point of contact (i.e., [name], [name]) of C-SSRS outcome. Threshold's research staff should follow up with participant's clinical team.

### Emergency procedures

- NU staff should alert the Research Manager and primary Thresholds research contact about the concern (provide with demographics and relevant medical information such as suicidal and/or homicidal ideation/intent, diagnosis, medical condition).
- Thresholds research staff should contact participant's clinical team and obtain recommended next steps (i.e. go immediately to ED, wait for clinical staff to arrive, or schedule an appointment for the participant with clinical provider).
- Pending recommendation from Thresholds clinical provider (if recommended to make appointment with provider or go immediately to Emergency Department), discuss the issue with all relevant research staff and participant.
- If recommended to make appointment with provider, ensure that appointment is secure promptly and that date, time, location, and name of provider appointment are documented before participant leaves the research premises.
- If recommended to go immediately to ED:
  - Call 911.
  - In the case of an involuntary hospitalization/ED evaluation: call Police; a research team member should go with police since "Petition" is required.
  - In the case of a voluntary hospitalization/ED evaluation: call Ambulance to escort thepatient.
  - In the case of suicidal ideation/intent, a research team member must watch (i.e., must have eyes on) the participant until Police/Security/Ambulance arrives.

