## D. 3. Combined Baseline Visit 2/3 for Thresholds' Clients (completed at Northwestern University or at Threshold's location) will require participants to complete:

1. Employment History Interview (EHI) The EHI will assess competitive work history data: length of time since last full-time (or any) employment, number of days employed in the past 5 years, history of prior interview training, and number of job interviews completed in the past three months. The EHI will also assess current housing status, income, and criminal justice history.

2. Brief Psychiatric Rating Scale (BPRS) (lasting approximately 30 minutes). The BPRS will assess psychiatric symptoms including somatic concern, anxiety, emotional withdrawal, conceptual disorganization, guilt feelings, tension, mannerisms and posturing, grandiosity, depressive mood, hostility, suspiciousness, hallucinatory behavior, motor retardation, uncooperativeness, unusual thought content, blunted affect, excitement, and disorientation.

3. The Beck Depression Inventory (approximately 15 minutes) is a self-report of depression symptoms.

A rating of "2 ("I would like to kill myself," or 3 ("I would kill myself if I had the chance" on item 9 on the Beck Depression Inventory indicates presence of suicidal ideation.

When a participant meets one of the above cutoff scores, the research staff will administer the **Columbia-Suicide Severity Rating Scale (C-SSRS).** A total score of 4 or higher on the "Intensity of Ideation" section of this measure will indicate whether or not the participant has a level of suicidal risk that requires further consideration. The procedures outlined in section 10 (Risks to Participants) will be followed if a participant scores 4 or higher.

4. MATRICS Consensus Cognitive Battery (MCCB) (approximately 1 hour) . The MCCB is a standardized cognitive battery for use with adults with schizophrenia and related disorders.

5. Participants will receive a break and be provided a healthy snack.

6. WHO Quality of Life-BREF (WHOQOL-BREF) (approximately 10 minutes) . The WHOQOL-BREF is a brief quality of life survey.

7. The 12-item Short Form Health Survey (SF-12) (approximately 10 minutes) . This assessment is a brief survey about the participant's physical health.

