# D. 6. Visit 10 (Post-test Visit completed at Northwestern University, at a Threshold's Odgen location, or via a phone call or video-conference) will be a repeat of the following measures (see D.2. and D.3. for more details):

- 1. Brief Psychiatric Rating Scale (BPRS)
- 2. Beck Depression Inventory (BDI)
  - a. Columbia-Suicide Severity Rating Scale (C-SSRS) if triggered by BDI scores
- 3. Job-Interview Role Plays
- 4. Social Skills Performance Assessment(SSPA)
- 5. Employment History Interview (follow-up version)
- 6. Job Interview Self-Efficacy
- 7. Personal Report of Job Interview Anxiety
- 8. Intrinsic Motivation Inventory
- 9. Technology Comfort Level Questionnaire is a 6-item measure that assesses one's comfort level with computer technology (approximately 5 minutes).

In addition, VR trainees will complete the 5 item Training Experience Questionnaire (TEQ; < 5 minutes). The

Posttest Visit 10 will last approximately 150 minutes or 2 hours and 30 minutes. Participants will be paid \$50.

**D. 7. Monthly Check-in Telephone Calls for Thresholds Clients (completed via telephone) will involve a brief (<10minutes) telephone survey asking about participants' potential interview or job-related activity in the past month.** These calls will be scheduled at monthly intervals after completion of post-test until the 6-Month Follow-Up (see D. 9.), for a total of 5 calls.

D. 8. Visit 11 (6-Month Follow-Up Visit completed at Northwestern University, a Threshold's Ogden location or via a phone call or video-conference) will be a repeat of the following measures (see D.2. and D.3. for more details):

- 1. Brief Psychiatric Rating Scale (BPRS)
- 2. AUDIT-SR
- 3. DAST-10
- 4. WHOQOL-BREF
- 5. SF-36
- 6. Beck Depression Inventory
  - a. Columbia-Suicide Severity Rating Scale (C-SSRS) if triggered by BDI scores
- 7. Employment History Interview (follow-up version)
- 8. Job Interview Self-Efficacy
- 9. Personal Report of Job Interview Anxiety
- 10. Intrinsic Motivation Inventory

Participants will also complete the SF-12 health questionnaire about their physical health and the Employment History Follow-up interview that will assess how many job interviews were completed, total hours worked, how many jobs were offered (and accepted), hourly wage, type of job, jobs terminated (and why).

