Alternatively, if participants are unable to attend visit 10 and/or 11 in person, the study team will schedule a series of brief phone calls in order to collect the self-reported study data by phone. In addition, the study team will offer participants the opportunity to complete their follow-up role-play assessment by means of a videoconference through BlueJeans. The BlueJeans videoconference will then be recorded by the University of Michigan research team that is approved for this study and the recordings will be stored using the previously approved methods for storing audiovisual data.

Alternatively, if the participants do not want to complete the videoconference then the participants will be offered the opportunity to complete their follow-up role-play assessment by means of a teleconference through BlueJeans. The BlueJeans teleconference will then be recorded by the University of Michigan research team that is approved for this study and the recordings will be stored using the previously approved methods for storing audiovisual data.

**D. 9. Monthly Check-in Telephone Calls for Thresholds Clients (completed via telephone) will be a repeat of procedures of the Monthly Check-in Telephone Calls for Thresholds Clients (see D. 8.).** These calls will be scheduled at monthly intervals after completion of the 6-month follow-up until the 9-month follow-up (see D. 11.), for a total of 2 calls.

D. 10. The 9-Month Follow-Up for Thresholds Clients (completed via telephone) will include only the Follow-up Employment History interview that will assess how many job interviews were completed, total hours worked, how many jobs were offered (and accepted), hourly wage, type of job, jobs terminated (and why).

The 9-Month Follow-Up Telephone Call will last approximately 10 minutes. If participants complete at least one of the two check-in calls between the 6-Month and 9-Month Follow-Up calls, they will be paid \$10 by Thresholds after the completion of the 9-Month Follow-Up call.

**D. 11. Participation Complete.** If a Thresholds client becomes employed prior to the 6-month follow-up call, they will still participate in monthly check-in phone calls and the 6-month follow-up. Their participation in the study will then be complete after completing the 6 month visit.

If the participant becomes employed between the 6- and 9-month follow-up calls, the participant will be asked additional questions on their next check-in call, which will be their last check-in.

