### • If at other Thresholds Location

- Inform relevant building staff/front desk staff that the police and/or an ambulance are on the way. Ensure that they know where you are in the building so that they can escort emergency personnel to you when they arrive.
- A research team member must provide documentation (i.e., progress note) from the investigator to give to the police/emergency personnel regarding the investigator recommendation.
- Document which hospital participant is being taken to then contact that hospital to provide the ED staff which all necessary information.
- Follow up with crisis team/on call resident at hospital to give information about the participant
- Email Principal Investigators and Thresholds Site PI to notify them that emergency procedures took place.
- Follow up with participant's clinical team to let them know what emergency procedures took place.
- Follow-up with participant within 24 hours to verify they were able to access the help they needed, or follow-up with ED to verify if participant was admitted to hospital.
- Document all activities for the study file and for correspondence with clinicians/IRB.

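### Visits 10 and 11 may be held by phone or video with the suicide-risk trigger still listed, but several emergency steps and all three location lists assume an on-site participant

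*Combined protocol and SAP*

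**What the plan says.** **Remote visits.** In section 4.0, the D.6 heading allows Visit 10 "at a Threshold's Odgen location, or via a phone call or video-conference) will be a repeat of the following measures". The D.8 heading gives Visit 11 the same latitude: "a Threshold's Ogden location or via a phone call or video-conference) will be a repeat of the following measures". Both lists include the BDI, followed by "Columbia-Suicide Severity Rating Scale (C-SSRS) if triggered by BDI scores". For participants who cannot attend, the text after the scheduling rules in D.8 says that "the study team will schedule a series of brief phone calls in order to collect the self-reported study data by phone". It also offers the role-plays by videoconference or teleconference, recorded by the University of Michigan team. Section 8.0 D (consent addendum) describes these remote visits as abbreviated, without listing which measures are kept.

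**Trigger.** Section 10.0 sends a BDI item 9 rating of 2 or 3, or another indication of suicidal ideation, to the C-SSRS. An intensity score of 4 or higher then leads to the emergency procedures. Visit mode is not mentioned.

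**Response.** The emergency procedures include the watch quoted as "a research team member must watch (i.e., must have eyes on) the participant until Police/Security/Ambulance arrives" and a requirement that appointment details "are documented before participant leaves the research premises". In an involuntary case a team member should also go with the police. Three location lists follow: Northwestern, the Thresholds Ogden site, and "If at other Thresholds Location".

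**The concern.** The option to hold Visits 10 and 11 remotely does not appear to have been carried through to section 10.0. A participant screened by phone can cross the same cut-off as one in the clinic, and staff would then open a procedure written for someone in the building.

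Two things are at stake. First, some instructions, including one worded as mandatory, cannot be carried out by telephone. Staff must then improvise or record a deviation at a moment when the procedure should be unambiguous. Second, a call to emergency services needs a place to send help, and nothing in the remote-visit text or in section 10.0 asks staff to confirm where the participant is.

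Visits 10 and 11 are also the only visits after randomisation with a scheduled BDI and C-SSRS screen. The monthly calls and the 9-month call list none.

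**Working it through.** No arithmetic is involved beyond counting. The check sets the passages side by side.

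**1. Does a remote visit reach the trigger?** Section 4.0 D.3 describes the instrument: "The Beck Depression Inventory (approximately 15 minutes) is a self-report of depression symptoms". The text under D.8 has self-reported data collected by phone, and both visit lists contain the BDI with no remote exception. The natural reading is that the BDI is given remotely. This is an inference, because section 8.0 D calls the remote visits abbreviated and does not say what is dropped. There is a second route: section 10.0 allows the C-SSRS after distress during other procedures, including role-plays, and role-plays may be done by video or teleconference.

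**2. Does the trigger depend on visit mode?** No. The instruction to proceed at a score of 4 or higher is unconditional.

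**3. Which steps in the general emergency procedures need presence?**

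| Step | Needs participant on site? |
|---|---|
| Alert the Research Manager and Thresholds contact | No |
| Obtain next steps from the clinical team | No |
| Discuss the recommendation with staff and participant | No |
| Secure and document an appointment before departure | The timing does; making the appointment does not |
| Call 911, police or ambulance | No, but a location is needed |
| Go with police (involuntary case) | Yes |
| Watch until responders arrive (suicidal ideation or intent) | Yes by telephone; arguably met in part on video |

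Three steps therefore presuppose presence.

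**4. What do the location lists add?** Each of the three has 8 items. In each, 2 are tied to a building or to handing over a document: alerting security or building staff, and giving a progress note to responders. The other 8 − 2 = 6 concern hospital contact, notifications, the 24-hour follow-up and documentation, and can be done by phone or email. All three lists are on site (3 of 3), and none covers a participant at home or elsewhere.

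**5. Is the participant's location known?** Contact information is taken at the baseline visit (D.2), and Visit 11 falls about six months after the post-test visit (section F.1). The scheduling rules in D.8 describe the population as hard to reach, and section 16.0 notes that some Thresholds clients experience chronic homelessness. A recorded address may therefore not be where the participant is during the call. No step asks.

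**6. Who acts?** The named duties in the general emergency procedures fall to Northwestern and Thresholds staff; others fall to an unspecified research team member. The text does not say what a Michigan staff member on a remote role-play should do, and section 13.0 limits access to protected information to the Northwestern and Thresholds investigators and teams.

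**The case against.** The strongest reply is that the general procedure still works for a remote participant. After the internal alert, staff contact the treating team for next steps, which needs no shared location; most later items can also be done by phone. The location lists add building logistics and are not the whole instruction. All of this stands.

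A reader might go further in several ways that the documents do not support:

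- *That every emergency step assumes presence.* The table above shows otherwise.
- *That the watch rule is impossible for anyone seen remotely.* It applies only after a positive C-SSRS, an ED recommendation, and suicidal ideation or intent. Video may satisfy it in part.
- *That remote use of the BDI is stated as fact.* It is a strong inference, qualified by the word abbreviated in section 8.0 D.
- *That staff would have no idea where to send help.* Baseline contact details exist, letters are posted to participants, and the clinical team is contacted. What is missing is a check of current location.
- *That the Michigan team is shut out of the response.* Some duties are assigned to any research team member, so the gap is one of clarity.
- *That an assumed share of remote visits gives the number affected.* That would count everyone screened remotely. The affected group is those who screen positive, for which the documents give no rate.

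The consent addendum read to remote participants is not available for this review and may contain safety wording. Unless it amends section 10.0, the instructions that staff follow would still lack a remote route.

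**Conclusion.** The point holds in a limited form. The protocol allows remote Visits 10 and 11 without exempting them from the suicide-risk trigger. Three steps of the general emergency procedures and all three location lists presuppose an on-site participant. None addresses phone or video contact, and no step confirms current location. The remaining steps are usable remotely.

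This rests on reading the BDI as kept in the abbreviated remote visit; if it is dropped, the route through other indications of risk or distress remains. The number of clients affected cannot be estimated from the documents. The issue concerns participant safety and the coherence of the procedures. It does not bear on the trial's estimates or tests. It should be corrected before further remote visits, mainly because the correction is cheap.

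**What to change.** The sponsor and the site's clinical leads should reconcile the remote-visit text (section 4.0 D.6 and D.8, and section 8.0 D) with section 10.0, from the C-SSRS cut-off through the three location lists, so that the procedures cover remote contacts. The clinical response is theirs to set, and none is proposed here. The same amendment should state which measures the abbreviated visit retains.

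Two operational additions would help:

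- At the start of each remote Visit 10 or 11 contact, confirm and record the participant's current location and a call-back number.
- State which team member makes each notification, including what any University of Michigan staff on the call should do.

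The cost is one protocol amendment and one added script question for the participant to answer at each remote contact.
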